2.0 Background

2.1 Overview

The myelodysplastic syndromes (MDS) are bone marrow failure disorders that primarily affect the elderly. Up to 50,000 people are diagnosed with MDS each year in the United States^{1,2}, making them one of the most common hematologic malignancies. The disease can be clinically devastating, as patients who do not succumb to infections or bleeding often develop acute leukemia. Many also experience a severe decline in their QOL.^{3,4} The likelihood of increasing MDS incidence as the population ages has prompted the American Society of Hematology to include “finding an effective and personalized treatment” for MDS as one of its top research priority areas.⁵

While several potentially disease-modifying medications were approved in the mid-2000s, progress has been slower since,⁶ and red cell transfusions remain a mainstay of care. Unfortunately, chronic red cell transfusions have many disadvantages, including iron overload,⁷ decreased overall QOL among the transfusion-dependent,⁸ and increased stress on the national blood supply.⁹ Moreover, some patients experience improved QOL after transfusions, others do not.

While compromised QOL is often invoked to justify transfusions for patients with MDS, the question of whether or not QOL improves after transfusion remains unanswered due to several barriers.^{10,11} First, until recently, a rigorous tool to assess MDS-specific QOL did not exist. Second, research assessing when QOL concerns might outweigh physiologic ones has been limited by a lack of consensus regarding a minimum hemoglobin (Hb) that is safe for outpatients with MDS. Third, it has been difficult for researchers to systematically identify patients who would benefit from formal QOL assessment, such as those starting transfusions and the transfusion-dependent. Finally, while some patients likely experience improved QOL after transfusion, others do not, even at the same level of Hb. We thus propose that the key question is not whether transfusions improve QOL, **but how to tailor transfusion decisions to the QOL changes experienced by individual patients living with MDS.**

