3.2 Inclusion/Exclusion Criteria

Inclusion criteria:

1. Age \geq 18 years of age
2. Patients with MDS, including t-MDS and MDS/MPN
3. Transfusion-naive group: approaching Hb of 8.5 g/dL during enrollment period
 - a. Ideally never-transfused (have never received red cell transfusion)
 - b. If not never-transfused, participants are also eligible for inclusion in this group if they have not been transfused with red cells within last 8 weeks
4. Transfusion-dependent group: Patients with \geq 1 transfusion scheduled during 8-week period prior to enrollment
5. Ability to read and understand English

Exclusion criteria:

1. Age $<$ 18 years
2. Cr $>$ 2
3. Known CHF
4. Unstable Angina
5. Hb level below 7.5 g/dL
6. No plans for potential future outpatient transfusion.

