8.0 Study Endpoints

8.1 Study Outcomes

Primary Endpoints

Subjects will be compared with historical controls (matched for transfusion group; IPSS-R; pre-transfusion Hb; and institution) seen between 2015 and 2017. For the transfusion-naïve, the primary outcome will be receipt of second transfusion (yes/no) within 8 weeks following the index transfusion. For the transfusion-dependent, the primary outcome will be defined as number of units pRBCs received within 8 weeks following the index transfusion. For both groups, we will also compare the number of hospitalizations and clinic visits during the 8 weeks after index transfusion (Table).

Secondary Endpoints

Secondary endpoints include decisional regret, perceptions of care, and perceived stress by the associated scales at two months post-transfusion (Table 1).

Table. Primary and Secondary Outcomes, Measured at Two Months after PTQA

Primary	Presence of second transfusion after PTQA (for those undergoing first transfusion) Number of red cell units used since PTQA (for transfusion-dependent) Number of hospitalizations since PTQA Number of clinic visits since PTQA
Secondary	Decisional Regret Decision Regret Scale. ³² 5-item scale provides indicator of health care decision regret; will be tailored to measure regret about transfusion decisions. Perceptions of Care “About Your Care” Domain of Prior DFCI Survey. We previously developed ³³ a 6-item domain based on the Consumer Assessment of Healthcare Providers and Systems Survey “health status” “access,” and “communication” domains. ³⁴ Perceived Stress PSS-4. ³⁵⁻³⁷ The PSS-4 was designed for use with patients with at least a junior high school education, and takes 3 minutes to complete. It contains four questions about feelings of control and overall stress, with simple response alternatives.

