9.4 Data Collection

Data will be collected via medical record reviews, the QUALMS, and several other survey instruments.

Primary medical record review will include:

- Sociodemographic information
- Information regarding patients' MDS diagnosis, including IPSS-R score
- The number/frequency of transfusions prior to index transfusion (for transfusion-dependent patients)
- Hemoglobin level prior to index transfusion

Secondary medical record review will include:

- The presence of a second transfusion since index transfusion (for those who are starting transfusion)
- The number of red cell units used since index transfusion (for those who are transfusion-dependent)
- The number of hospitalizations since index transfusion
- The number of clinic visits since index transfusion

Survey instruments will include:

- The QUALMS to assess pre- and post-transfusion MDS-related QOL (see Appendix A)
- The Decision Regret Scale, "About Your Care" domain of prior DFCI survey, and the PSS-4 to assess secondary outcomes related to decisional regret, perception of care, and perceived stress (see Appendix B)

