11.0 Data Management and Confidentiality

11.1 Data Analysis Plan

Feasibility

Feasibility will be characterized by calculating (1) the proportion of enrolled patients out of all patients approached, and (2) the proportion of patients who completed both the pre- and post-transfusion QUALMS surveys out of all enrolled patients. A convenience sample of 60 evaluable patients will be enrolled to the study. To reach this goal, we will enroll 90 participants total, with the expectation that some patients will not be able to complete the study protocol, despite being eligible at the time of consent (e.g., do not end up requiring future transfusions). If the observed survey completion rate is 50% (i.e. 30/60), then this observed rate is consistent, with 95% confidence, with the true survey completion rate being as low as 38% or as high as 62%.

Clinical and Utilization Outcomes

To be assessed for clinical and utilization outcomes, participants must have completed a pre-transfusion QUALMS, received an index transfusion, and completed a post-transfusion QUALMS. Each of the 60 enrolled evaluable patients will be matched 1:1 to historical controls seen between 2015 and 2017, for a matched sample size of 120 patients total. Subjects will be matched for transfusion group, IPSS-R, pre-transfusion Hb, and institution). Comparative analyses will be conducted separately by transfusion group. For the transfusion-naive, the primary outcome will be receipt of second transfusion (yes/no) within two months following the first transfusion. For the transfusion-dependent, the primary outcome will be defined as number of units pRBCs received within two months following the next transfusion.

For both groups, we will also compare the number of hospitalizations and clinic visits two months after index transfusion (Table).

PTQA Utilization and Patient-Reported Outcomes

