37	...were you afraid that your MDS treatment would stop working? (check here if not applicable because you are not currently being treated)					
38	...have you been too tired to take care of a family member or loved one? (check here if not applicable because you are not providing such care)					

[figure not shown]

PROTOCOL TITLE: A New Paradigm of Transfusion Decision Support for Patients with MDS:
Using Peri-Transfusion Quality of Life Assessments (PTQAs)

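### MDS-directed therapy at index is not restricted, matched on or named in the chart review, so a systematic difference from the 2015–2017 controls could create or hide a PTQA effect

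*Protocol*

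**What the plan says.** Protocol 8.1 defines the primary comparison: "Subjects will be compared with historical controls (matched for transfusion group; IPSS-R; pre-transfusion Hb; and institution) seen between 2015 and 2017". Section 11.1 repeats the four factors ("Subjects will be matched for transfusion group, IPSS-R, pre-transfusion Hb, and institution") and fixes a 1:1 ratio. Section 23.2 names transfusion group alone.

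Eligibility in 3.2 is broad: "Patients with MDS, including t-MDS and MDS/MPN". No criterion excludes MDS-directed therapy or asks that it be stable.

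The disease item in the chart review (9.4) reads: "Information regarding patients' MDS diagnosis, including IPSS-R score". The other items are sociodemographics, transfusion number or frequency before index (dependent group only), pre-index haemoglobin and the utilization outcomes. Treatment is not named.

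The protocol nevertheless expects treated patients. Section 2.1 notes that "several potentially disease-modifying medications were approved in the mid-2000s". QUALMS item 37 asks "were you afraid that your MDS treatment would stop working" and offers a box for people not on treatment. Item 11 of the two-month survey (Appendix E) asks for a rating of the doctor prescribing chemotherapy or hormonal therapy.

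**The concern.** The outcomes are units of red cells, receipt of a second transfusion, hospitalizations and clinic visits over 8 weeks. Starting, changing or stopping MDS-directed therapy can plausibly alter red cell need within that window, and giving it generates visits. This is clinical reasoning; the documents put no figure on it.

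The arms are not randomised, so nothing in the design balances therapy between participants and controls. IPSS-R, haemoglobin and institution do not identify it: two patients with the same values can be untreated, on established therapy or just starting. If the cohorts differ systematically in therapy, the difference is attributed to PTQA. As the protocol stands, no therapy variable is planned for both arms with which to see or correct this.

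**Working it through.** **Step 1. Where therapy could enter the comparison.**

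| Route | Protocol | Therapy covered? |
|---|---|---|
| Eligibility | 3.2 | No |
| Matching | 8.1, 11.1 | No |
| Chart review | 9.4 | Not named |
| QUALMS item 37 box | Appendix B | Participants only; no agent, no dates |
| Prior transfusion frequency | 9.4 | Indirect; dependent group only; not a matching factor |

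**Step 2. The plan's own figures (11.2).** For the dependent group the inputs are 30 per arm, means 8.0 and 6.5, SD 2.0 and 5% type I error (taken as two-sided; the protocol does not say).
- Standard error = 2.0 × √(2/30) = 0.516.
- Power = Φ(1.5/0.516 − 1.96) = Φ(0.945) = 82.8%, which agrees with the stated 83%.
- Smallest difference reaching significance ≈ 1.96 × 0.516 = 1.01 units.

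For the naive group (100% to 70%, 30 per arm), the continuity-corrected formula gives 84.8%, which agrees with the stated 85%. Both calculations treat the whole cohort difference as due to PTQA.

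**Step 3. What a systematic therapy difference would do to mean units.** The shift equals the difference in share treated times the effect of therapy on 8-week units. The documents give neither input. With an assumed 20-point difference and an assumed effect of 2 to 4 units:
- 0.20 × 2 = 0.4 units, and 0.4/1.5 = 27% of the target difference.
- 0.20 × 4 = 0.8 units, and 0.8/1.5 = 53% of the target difference.

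*If the shift favours PTQA and PTQA does nothing*, the two-sided 5% t-test (58 df, SD 2.0) rejects in 11.9% of studies at 0.4 units and 33.2% at 0.8.

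*If the shift works against PTQA and the true effect is 1.5 units*, the expected difference falls to 1.1 or 0.7:
- Φ(1.1/0.516 − 1.96) = Φ(0.170) ≈ 57% power.
- Φ(0.7/0.516 − 1.96) = Φ(−0.604) ≈ 27% power.

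**Step 4. How far the assumption depends on its inputs.** Over differences of 10 to 30 points and effects of 2 to 4 units, the shift runs from 0.2 to 1.2 units and the false-positive rate from 6.7% to 62.8%. The upper end strains the plan's own SD. A 4-unit effect with half the patients treated contributes 0.5 × 0.5 × 16 = 4.0 to the variance, which is all of 2.0². With 30% treated it contributes 0.3 × 0.7 × 16 = 3.36, or 84%. A 2-unit effect with half treated contributes 1.0, or 25%, and fits easily. The lower part of the range is therefore more consistent with 11.2.

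**Step 5. Naive group.** If controls are at 100% and participants at 90%, 85% or 80% for reasons unrelated to PTQA, Fisher's exact test is significant in 7%, 29% or 57% of studies. This shows how the test responds to such a shift; it does not predict one.

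**The case against.** The case on the other side has real force.

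- **No evidence of imbalance.** Controls come from the same institutions in the years shortly before the study, and 2.1 says progress has slowed since the mid-2000s approvals. That makes drift from new drugs less likely. It does not address who is on, starting or stopping therapy at index.
- **A proxy exists.** Prior transfusion frequency reflects recent red cell need, including the effect of established therapy, in the group whose outcome is units. This stands in part: the variable is not used for matching, is listed only for the dependent group, and lags behind a recent change in therapy.
- **The SAP can handle it.** Covariates are properly an SAP matter. The SAP still needs a variable abstracted in the same way in both cohorts, and the protocol is where the matching factors and data items are set.
- **It is a pilot.** True, but 8.1 labels the comparison primary and 11.2 powers it.
- **The effect sizes are assumed.** Correct. Effects in opposite directions could also partly cancel.

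Three stronger readings are tempting and are not supported. A reader might take the 9.4 list as exhaustive and the confounding as beyond repair; the wording is inclusive, and therapy remains in the medical records, from which it could still be abstracted for both cohorts. A reader might say therapy is wholly unrecorded; the item 37 box is a partial exception. A reader might add that groups of 30 can differ in therapy by chance; that is sampling variation, already covered by the outcome SD and the 5% error rate, and is not bias.

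**Conclusion.** The point holds as a gap in the planned control of confounding. Therapy at index is not restricted, not matched on and not named for abstraction, although the protocol itself anticipates treated patients. A systematic difference between the cohorts could create or hide an apparent PTQA effect in the primary comparisons.

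The documents do not show that such a difference exists, nor its direction or size. The 0.4 to 0.8 unit shift against the 1.5-unit target rests wholly on the assumed 20-point difference and 2 to 4 unit effect. The conclusion does not require therapy to be the main driver of transfusion need; it requires only that therapy can affect the outcomes and may differ between the cohorts. The change is worth making because it is cheap and the comparison is otherwise hard to interpret, not because bias has been demonstrated.

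**What to change.** **Section 9.4.** Add MDS-directed therapy and erythropoiesis-stimulating agent status at the index transfusion, abstracted by the same rules for participants and controls: none; ongoing; or started, changed or stopped in the prior 8 weeks.

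**Section 11.1.** Report the balance of this variable between cohorts by transfusion group, and adjust the primary comparisons for therapy at index (yes/no). Use it as a matching factor only where matches allow; with 30 per group across three institutions, a mandatory fifth factor could leave participants unmatched. In the naive group the planning rate for controls is 100%, so an ordinary logistic model may not be estimable and a stratified risk difference would be safer. Therapy started after index may itself follow from the PTQA report, so describe it but do not adjust for it.

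**Cost.** A small amount of extra abstraction in a chart review already planned, including an 8-week look-back, and one covariate. No patient's treatment is affected.

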1.0 Objectives

1.1 Study Aims

The goal of this multi-center study is to determine how to tailor blood transfusion decisions to the quality of life (QOL) changes experienced by individual patients with myelodysplastic syndromes (MDS). We will assess this by piloting a peri-transfusion QOL assessment (PTQA) approach. The PTQA involves administering a QOL questionnaire (see Appendix A) to study participants before and after an upcoming transfusion appointment and comparing QOL scores.

Specific Aim 1

Assess the feasibility of PTQA. We will assess the feasibility of this new paradigm of decision support by determining the enrollment yield as a percentage of all patients approached. We will also assess feasibility by calculating the proportion of enrolled participants who complete both the pre- and post-transfusion the Quality of Life in Myelodysplasia Scale (QUALMS).

Specific Aim 2

Assess the potential usefulness of PTQA in improving clinical and utilization outcomes. We will use medical record review and match our participants to historical controls (matched for transfusion group; IPSS-R; pre-transfusion Hb; and institution) to assess our primary outcomes, which are:

1. The presence of second transfusion after PTQA (for transfusion-naive)
2. The number of red cell units used after PTQA (for transfusion-dependent)
3. The number of hospitalizations after PTQA (for both transfusion groups)
4. The number of clinic visits after PTQA (for both transfusion groups)

Specific Aim 3

Explore the potential impact of PTQA on patient-reported outcomes. At 8 weeks post-transfusion, we will send participants a follow-up questionnaire (see Appendix B) to assess the following secondary outcomes:

1. PTQA utilization
2. Decisional regret
3. Perception of care
4. Perceived stress

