9.2 Study Procedures

Please see study schema (Appendix C) for study flow.

Pre-Transfusion

- Once identified by Epic scheduling report, provider suggestion, or study-specific Epic Workbench report, eligible patients will be approached for consent discussion at an appointment with their provider.
 - Patients with Hb approaching 8.5 g/dL will be approached at an appointment prior to an upcoming transfusion.
 - Patients that are transfusion-dependent will be approached at an upcoming appointment with their provider or during a transfusion appointment.
- During this initial encounter, consenting participants will be given a study packet containing a paper copy of the QUALMS. Study participants will be instructed to fill out the survey on the day before their upcoming pRBC transfusion.

**PROTOCOL TITLE: A New Paradigm of Transfusion Decision Support for Patients with MDS:
Using Peri-Transfusion Quality of Life Assessments (PTQAs)**

3. Study participants will indicate whether they would like to receive PTQA reports in person, via mail, or via email.
4. Site RAs will call study participants using script (see Appendix D) on the day prior to an upcoming transfusion to remind them to complete the QUALMS and bring it with them to their transfusion.
5. Note: Index transfusion is defined as any upcoming transfusion appointment for which the participant has completed both the pre- and post-transfusion QUALMS questionnaires.
 - If a participant does not complete the pre-transfusion questionnaire for any reason (i.e., participant forgot to complete at home or forgot to bring in), then the RA may ask the participant to complete the questionnaire at home prior to a subsequent transfusion appointment. This subsequent transfusion will become the index transfusion.
 - If a participant does not complete the pre-transfusion QUALMS at home prior to the appointment and there are extenuating circumstances (i.e., participant does not regularly receive transfusions at the site), then the RA may ask the participant to complete the questionnaire in clinic before his/her planned index transfusion.

Post-Transfusion

6. On the day of transfusion, the site RA will collect the completed pre-transfusion QUALMS survey. Study participants will then receive a second paper copy of the QUALMS, along with a stamped envelope addressed to the appropriate site.

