7. Participants will be instructed to complete this survey exactly one week after transfusion and return it using the pre-addressed, pre-stamped envelope.
8. Site RAs will call participants using script (see Appendix D) to remind them to complete the QUALMS survey exactly one week after transfusion.
 - The window may increase up to one extra week to accommodate for circumstances where the patient is unable to complete the post-transfusion QUALMS (i.e., participant does not feel well or participant forgot).

PTQA Report

9. Once received, the second assessment will be scored and compared with the first, and both the patient and provider will be sent a report with the results. The QUALMS validation study suggested that a clinically meaningful difference on the instrument is between 5 and 10 points;¹² For this study:
 - A post-transfusion score that is within 5 points of the pre-transfusion score will indicate a stable QOL
 - A post-transfusion score that increases by 5 or more points will indicate a clinically significant improvement in QOL
 - A post-transfusion score that decreases by 5 or more points will indicate a clinically significant decline in QOL
10. In our report, we will include language that encourages patient and providers to use these results to inform their next transfusion decision, specifically suggesting that transfusion be halted or decreased in frequency if QOL has worsened.

**PROTOCOL TITLE: A New Paradigm of Transfusion Decision Support for Patients with MDS:
Using Peri-Transfusion Quality of Life Assessments (PTQAs)**

Secondary Outcomes Assessment

11. At 8 weeks post-transfusion, all participants will be sent a survey (Appendix B) to assess the utilization of the PTQA and patients' decisional regret, perceptions of care, and perceived stress.

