We may find that patients and hematologists do not use the information in their PTQA reports to truly affect decision-making, as both may be anxious to forgo transfusions despite the fact that QOL did not improve. We plan to assess this parameter at two months post-transfusion by asking participants whether they discussed the PTQA report with their physician (see Appendix B). To help prevent the PTQA going unused, we will make sure that providers at each site have access to the consensus Hb data from our previous qualitative study (Protocol 18-064). These results will be disseminated to providers prior to study initiation. In addition, we will work closely with the DFCI Adult Patient and Family Advisory Council (PFAC) to vet the routine language in our PTQA patient reports so that is optimally educational and anxiety-reducing.

PROTOCOL TITLE: A New Paradigm of Transfusion Decision Support for Patients with MDS: Using Peri-Transfusion Quality of Life Assessments (PTQAs)

Exploratory analyses (e.g. descriptive statistics such as means and standard deviations) using the results from the follow-up survey (see Appendix B) will characterize decisional regret, perceptions of care, and perceived stress by the associated scales at two months post-transfusion (Table).

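### Aim 3 cannot show whether perceived stress or perception of care changed after PTQA, because each is measured once, at week 8, with nothing to compare it with

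*Protocol*

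**What the plan says.** The protocol (Section 1.1, Specific Aim 3) sets the purpose: "Explore the potential impact of PTQA on patient-reported outcomes". It lists four outcomes: PTQA utilization, decisional regret, perception of care and perceived stress.

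The timing is a single time point throughout. Section 8.1 states: "Secondary endpoints include decisional regret, perceptions of care, and perceived stress by the associated scales at two months post-transfusion". Section 9.2 states: "At 8 weeks post-transfusion, all participants will be sent a survey (Appendix B"). The survey itself is printed as Appendix E.

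Before transfusion only the QUALMS is collected. In Section 9.2, "consenting participants will be given a study packet containing a paper copy of the QUALMS". Section 9.4 gives the QUALMS alone a before-and-after role: "The QUALMS to assess pre- and post-transfusion MDS-related QOL". It lists the other scales without one.

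The analysis in Section 11.1 is "Exploratory analyses (e.g. descriptive statistics such as means and standard deviations"), which "will characterize decisional regret, perceptions of care, and perceived stress by the associated scales at two months post-transfusion (Table").

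**The concern.** An aim about impact, even a potential one explored descriptively, needs a reference value: an earlier score from the same patients or a score from comparable patients without PTQA. For stress and perception of care the protocol collects neither. A statistical analysis plan could add summaries of the data in hand, but it cannot create a baseline that was never collected.

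Stress is where this matters most. Two of the three report templates in Appendix C tell patients that quality of life did not improve after transfusion. Section 11.1 expects that patients and physicians may be anxious about forgoing transfusion, and wants report wording that reduces anxiety. Section 14.1 names emotional distress as the only foreseeable risk, although it attributes that to the questionnaires. The PSS-4 is the only stress scale given after the report, and without an earlier value it cannot show whether stress moved. The second QUALMS cannot stand in for it, because it is completed before the report exists.

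**Working it through.** The protocol states no precision or power for Aim 3, so there is no figure to reproduce. The check has three parts.

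**1. Is there a reference value for each Aim 3 outcome?**

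- *Perceived stress (PSS-4, one-month recall):* no pre-transfusion score and no control score. A baseline is possible.
- *Perception of care (12-month recall):* no pre-transfusion score and no control score.
- *Decisional regret:* Appendix E asks about the decision on future transfusions made after talking to the doctor. That decision does not exist at baseline, so a pre-value has no meaning.
- *PTQA utilization:* Appendix E items 1 to 3 ask whether the report was discussed, who raised it, and whether it affected the decision. No baseline is needed.

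The matched controls of 2015 to 2017 (Sections 1.1 and 11.1) come from medical record review and have no survey scores. The one comparison planned around the follow-up survey (Section 11.4) is of patient characteristics between those who do and do not complete it, not of scores.

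**2. What precision would a stress baseline give?**

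Inputs: 60 evaluable participants (Section 4.1), 30 per transfusion group (Section 9.1). The 95% half-width for a mean change, in units of the SD of the change, is t(0.975, n−1)/√n.

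- n = 60: 2.001/7.746 = 0.258, about 0.26 SD.
- n = 30: 2.045/5.477 = 0.373, about 0.37 SD.
- n = 45, as an assumed example of 25% non-return: 2.015/6.708 = 0.300, about 0.30 SD.

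To express this in SDs of the score itself, assume equal SDs at both times and a correlation ρ between them. The SD of the change is then √(2(1−ρ)) times the SD of the score. The protocol gives no ρ, so a range is shown. For n = 60:

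- ρ = 0.3: 0.258 × 1.183 = 0.31 SD
- ρ = 0.5: 0.258 × 1.000 = 0.26 SD
- ρ = 0.7: 0.258 × 0.775 = 0.20 SD

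As planned, the week-8 mean alone would have the same relative precision (±0.26 SD of the score at n = 60), but no change can be computed from it at any sample size.

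**3. Do the recall windows suit a before-after comparison?**

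- *PSS-4:* the recall is the last month. A form completed the day before transfusion looks back over the month before it. A form completed at week 8 looks back over roughly weeks 4 to 8. The second QUALMS is due at week 1, or week 2 with the permitted extension, so the later window should normally fall after the report. The two windows do not overlap.
- *Perception of care:* the recall is 12 months. For a survey completed when sent at week 8, 8/52 = 15% of the window follows the index transfusion. No report can exist before the one-week QUALMS, so at most about 7/52 = 13% follows the report. The score mostly reflects care before PTQA, and a baseline with the same recall would overlap it heavily.

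**The case against.** The strongest reply is that the plan does what it promises. These are secondary outcomes in a pilot, the aim speaks only of potential impact, and the analysis is labelled exploratory and descriptive. No test, effect estimate or power is claimed, so changing one word in the aim would remove the mismatch. That is fair. It makes this an inexpensive improvement rather than an error in the analysis. It does not remove the gap, because a lower standard of proof still needs something to compare with.

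A second reply is that a baseline would not isolate PTQA. A change in stress from just before transfusion to week 8 mixes the effect of the report with that of the transfusion, the course of the disease and regression to the mean. This stands in full, and it limits how the change may be described.

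A third reply is that week-8 scores could be split by report category or by whether the report was discussed, using data already collected. They could, and that is ordinary content for an analysis plan. But the category is itself defined by change in quality of life, so patients whose score declined may be more stressed whatever they are told. Such a split is optional and confounded, and does not replace a baseline.

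A reader might also infer that Aim 3 as a whole can reveal nothing about impact, or that all three scales are at fault for lacking a baseline. The protocol does not support either reading: utilization is asked directly, and regret concerns a decision made later.

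**Conclusion.** The point holds for perceived stress and perception of care only. Each has one week-8 score and no reference value, so the planned means and SDs describe a level and cannot show a change. For perception of care, the 12-month recall adds a second difficulty: at most about 15% of it follows the index transfusion.

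With a PSS-4 baseline, the change in stress could be estimated to about ±0.26 SD of the change overall, or ±0.37 SD in one transfusion group. Both figures assume that every evaluable participant returns both forms. Section 11.4 itself allows for non-completion and for deaths, so the actual intervals are likely to be wider.

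It would be wrong to infer that a baseline would let the study prove an effect of PTQA on stress. It would give an uncontrolled signal where there is now none. This is a modest improvement to a secondary aim. It does not affect the primary outcomes.

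**What to change.** - **Stress.** Add the PSS-4 to the pre-transfusion packet, to be completed with the first QUALMS for the index transfusion. Report the within-patient change to week 8 with a 95% confidence interval and the number of complete pairs. State that it is an uncontrolled before-after signal, mixed with the effect of transfusion and the course of the disease.
- **Perception of care and regret.** Reword Aim 3 so that it describes these two outcomes at 8 weeks. If the stress baseline is declined, use the same wording for stress.
- **Optional.** Summarize week-8 scores by report category and by Appendix E item 1, marked as descriptive and confounded.

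The cost is four items in an existing packet, an IRB amendment, and about 3 minutes per participant: Section 8.1 says the PSS-4 "takes 3 minutes to complete". No extra visit or procedure is needed. Participants who have already had their index transfusion when the amendment takes effect cannot contribute a baseline.
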